2. INTRODUCTION

2.1. Study Rationale

VXA-G1.1-NN is an E1/E3-deleted, replication-incompetent, adenovirus 5 (Ad5) vaccine vectors designed for use as an oral vaccine for the prevention of noroviral gastroenteritis caused by norovirus genogroups GI.1. The monovalent vaccine vector encodes the full-length of viral protein 1 (VP1) gene of Norwalk virus (Norovirus GI.1). The adjuvant consists of a double-stranded RNA Toll-like receptor 3 (TLR3) agonist which enhances immune induction to expressed antigen in the gut mucosa.

Noroviruses are a genetically diverse group of small, non-enveloped, single-stranded positive sense RNA viruses belonging to the Caliciviridae family (Bresee, 2002). Norovirus infections are a leading cause of sporadic and epidemic gastroenteritis across all age groups worldwide (Hoa Tran, 2013; de Graaf, 2016). There is an urgent public health need for rapid development of novel interventions to prevent the spread of this disease, including prophylactic measures, such as vaccines (Esposito, 2020).

A unique and advantageous immune response elicited by oral vaccination is the induction of antibodies derived from mucosal cells. Given that the mucosal route of immunization produces superior mucosal immunity compared to injected vaccines, it is hypothesized that VXA-G1.1-NN oral vaccine may enable higher degrees of mucosal protection against infection when compared to a parenteral immunization method.

VXA-G1.1-NN is designed to elicit both antibody and T cell responses, mucosally and systemically, to Norovirus GI.1 Norwalk VP1. Prior completed Phase 1 studies with the Vaxart Vector Adjuvant Antigen Standard Technology (VAASTTM) platform have demonstrated protective immunity to viruses, such as norovirus, influenza, and respiratory syncytial virus, with both systemic and mucosal immune responses against the antigen of choice (Kim, 2016; Kim, 2018; Liebowitz, 2020).

Clinical data is available from 3 Phase 1 studies (VXA- NVV-101, VXA-NVV-102, and VXA-NVV-103) which evaluated multiple single- and multi-dose ranging of the monovalent vaccine VXA-G1.1-NN in over 200 healthy young adult subjects (18 to 49 years old). These studies indicate that the vaccine was tolerated well and generated robust immune responses including systemic and mucosal antibodies as well as memory immunoglobulin A (IgA)/ immunoglobulin A (IgG). In addition to increase in serum blocking titer fifty assay (BT50) titers, vaccine recipients also developed mucosally primed VP1-specific circulating antibody secreting cells (ASCs), IgA⁺ memory B cells expressing gut-homing receptor (α 4 β 7), and fecal IgA, indicating substantial and local responses potentially relevant to prevent norovirus infection (Kim, 2018).

The current Phase 1b study is designed to assess the immunogenicity of VXA-G1.1-NN with repeat-dose administration at Day 1 and 2nd vaccination at Weeks 4, 8 or 12 (depending on Cohort assignment) in healthy adults aged 18-55, inclusive, with varying boost schedules.

2.2. Background

Noroviruses are a leading cause of foodborne disease and outbreaks of gastroenteritis worldwide and are responsible for substantial morbidity, mortality, and healthcare costs (Bányai, 2018). The

virus affects people of all ages; however, the incidence of disease is higher in younger children and in adults \geq 65 years old (Lopman, 2016; Esposito, 2020). Noroviruses are highly infectious with major mode of transmission by fecal-oral spread, usually via contaminated food or water (Teunis, 2008; de Graaf, 2016; Gaythorpe, 2018). The incubation period of norovirus is 10-51 hours.

Noroviruses are genetically diverse viruses. Genogroups I, II and IV are human-transmitted. Genogroup I and II account for the majority of norovirus outbreaks (Vega, 2014). Each genogroup is further divided into genotypes based on the similarity of the amino acid sequence of the major viral capsid protein, VP1. Genotypes GI.1 and GII.4 represent the genogroups responsible for most outbreaks and the majority of the disease burden globally (Lopman, 2016).

Norovirus causes extensive morbidity with clinical symptoms of nausea, vomiting, non-bloody diarrhea, and abdominal cramps. Fever, headache, and body aches have been reported as well. These symptoms usually last 2-4 days. Additionally, asymptomatic infections are estimated to occur in approximately one-third of infected people. Currently no specific therapy exists for norovirus gastroenteritis. The standard treatment is oral rehydration with fluids and electrolytes (Glass, 2009). There are currently no licensed vaccines for norovirus.

Norovirus is an enteric pathogen and infects the epithelial cells of the small intestine. Vaxart's platform is based on oral delivery of the vaccine to the intestinal mucosa, which is analogous to the natural route of norovirus infection and entry. Human and animal experience with Vaxart's orally administered platform has demonstrated that substantial transgene specific intestinal IgA responses can be generated in addition to systemic IgG responses to the expressed antigen (influenza HA and norovirus VP1). These platform attributes may allow for better protection against norovirus infection than an injected protein-based vaccine.

As indicated, VXA-G1.1-NN was well tolerated in 3 Phase 1 studies and generate robust immune responses. In study VXA-NVV-101, the primary immunological endpoint (increase in BT50 titers) was met in the high-dose group (P = 0.0003), with 78% showing a \geq 2-fold rise in titers after a single immunization (Kim, 2018). Statistically significant increases in geometric mean titers were also seen in Study VXA-NVV-103 with VXA-G1.1-NN compared with placebo (p=0.0008), with 43% of subjects showing a \geq 4-fold increase in titers post vaccination.

A detailed description of the chemistry, pharmacology, efficacy, and safety of VXA-G1.1-NN is provided in the Investigator's Brochure (IB).

2.3. Benefit/Risk Assessment

More detailed information about the known and expected benefits and risks and reasonably expected adverse events of VXA-G1.1-NN may be found in the IB.

Clinically Significant Risk	Summary of Data/Rationale for Risk	Mitigation Strategy
	Study Drug VXA-G1.1-NN	
Potential for vaccine related hypersensitivity, including anaphylaxis	Similar to other drugs, vaccines have the potential to cause allergic reactions. Vaccine components including immunizing antigens, adjuvants, culture derived proteins (e.g., gelatin) and other agents may have the potential to cause complications.	Monitor participants for any allergic reactions and onset of new illness during the active and follow-up period.
Potential for systemic and gastrointestinal events (fever, headache, myalgia, abdominal pain, anorexia, nausea, vomiting, vomiting, diarrhea, and malaise/fatigue) following vaccination.	These systemic events are common adverse reactions seen with other vaccines, as noted in the FDA Center for Biologics Evaluation and Research (CBER) guidelines on toxicity grading scales for healthy adult volunteers enrolled in preventive vaccine clinical studies. Given the route of delivery and mechanism of action for an ingestible vaccine, some additional GI events may also be observed.	Actively monitor systemic and GI-associated reactions (solicited symptoms) for 7 days following each study drug administration.
Potential for severe events of thrombosis in combination with thrombocytopenia (Thrombosis with thrombocytopenia syndrome, TTS), in some cases accompanied by bleeding, as reported in rare cases following vaccination with two injected adenovirus- vectored COVID-19 vaccines.	Severe cases of TTS have been reported following vaccination with two adenovirus- vectored COVID-19 vaccines: the AstraZeneca COVID-19 vaccine (ChAdOx1; replication-deficient chimpanzee adenoviral vector ChAdOx1) and the Johnson and Johnson COVID-19 vaccine (Ad26.COV2.S; replication-incompetent adenovirus serotype 26 vector). Reports include cases of thrombocytopenia in combination with arterial and venous thrombosis at unusual sites, such as cerebral venous sinus thrombosis (CVST) and splanchnic vein thrombosis, as well as more common sites such as veins of the lower extremity. Onset of symptoms associated with these AEs has typically occurred within 4 weeks after vaccination, and most commonly within 1-2 weeks after vaccination, although some cases have been reported mostly in women under 60 years of age, although cases have also been reported in men and in women older than 60 years. Some of these cases have been fatal. A causal relationship between these events and the two vaccines is considered plausible. The exact patho- physiology of TTS is still under investigation. At this time, a mechanism related to the adenovirus vectors cannot be excluded.	Exclude enrollment of participants at higher risk of clotting events per review of medical history, physical exam and safety laboratory tests at screening. Actively monitor for signs and symptoms of thromboembolism and/or thrombocytopenia. Study participants should be instructed to seek immediate medical attention if they develop symptoms including, but not limited to, shortness of breath, chest pain, leg pain and/or swelling, persistent abdominal pain, severe or persistent headaches, blurred vision or other vision changes, mental status changes or seizures, petechia, purpura beyond the site of vaccination, and/or easy bruising/ bleeding.

2.3.1. Benefit Assessment

Benefits to individual participants may include receipt of a potentially efficacious norovirus vaccine. Clinical data from Phase 1 studies demonstrated that VXA-G1.1-NN generated robust immune responses.

2.3.2. Overall Benefit/Risk Conclusion

Taking into account the measures to be utilized to minimize risk to participants taking part in this study, the potential risks identified in association with the VXA-G1.1-NN vaccine for the prevention of norovirus infection are justified as by the anticipated benefits that may be afforded to healthy stable adult participants.

3. OBJECTIVES AND ENDPOINTS

Objectives	Endpoints		
Primary			
• To evaluate the immunogenicity of VXA-G1.1-NN with repeat-dose administration at Day 1 and varying boost schedules (Week 4, 8 or 12 post initial dose) in healthy adults aged 18-55, inclusive	 VP1 specific IgA ASC by enzyme-linked immunospot (ELISpot) Norovirus G1.1 histo-blood group antigen (HBGA) blocking antibodies (BT50) VP1 specific serum IgG by Mesoscale Discovery (MSD) assay 		
Secondary			
• To assess the safety and tolerability of VXA- G1.1-NN with repeat-dose administration at varying boost schedules (Week 4, 8 or 12) in healthy adults aged 18-55, inclusive	 Frequency, duration, and severity of solicited symptoms of reactogenicity (local, systemic) for 1 week following each dose of study drug Frequency, duration, and severity of unsolicited serious AEs (SAEs), AEs of special interest (AESIs) and New Onset of Chronic Illness (NOCIs) through each Study Period (4 weeks post each vaccination) 		
Exploratory			
• To assess additional safety parameters	• Occurrence of clinically significant abnormalities in laboratory parameters (chemistry, hematology and urinalysis) at 1 week after each study drug dose and in vital signs immediately following each dose		
• To assess long-term safety of VXA- G1.1-NN through 6 months after last vaccination	• Frequency, duration, and severity of all SAEs, AESIs and NOCIs through 6 months after last vaccination		
 To assess additional immunogenicity parameters of VXA-G1.1-NN (Note: Additional exploratory immunogenicity assays may also be performed to further evaluate the activity of the VXA-G1.1-NN vaccine candidate) 	 VP1 specific IgG ASC VP1 specific serum IgA Ad5 neutralizing antibodies VP1 specific IgG and IgA memory B cells B cell immunophenotyping Saliva VP1 IgA Nasal Swab VP1 IgA 		

4. OVERALL STUDY DESIGN

This is an open-label, boost-optimization study of an adenoviral- vector based oral norovirus vaccine (VXA-G1.1-NN) expressing GI.1 VP1 administered orally to health adult participants 18-55, inclusive. This study will enroll approximately 30 participants in three cohorts stratified by varying boost vaccination schedules.

The study will include a Screening period, Active study period through 4 weeks post last vaccination dose (Week 8 for Cohort 1, Week 12 for Cohort 2 and Week 16 for Cohort 3), and a Follow-up period of 6 months post vaccination (Month 7 for Cohort 1, Month 8 for Cohort 2 and Month 9 for Cohort 3). Study assessments will be conducted as shown in the SoA in Section 1.2 (Table 2). In addition, participants will be contacted monthly by phone between site visits to monitor for safety as specified in the SoA.

After signing an informed consent, participants will undergo screening assessments to determine study eligibility over a 45-day screening period.

On Day 1, participants will be enrolled sequentially in order of eligibility. Participants may be assigned to cohorts based on their availability for the second dose (boost). Cohorts 3 and 2 may be enrolled prior to Cohort 1 to optimize the overall study timeline.

Group	Study Drug	Dose (IU ±0.5 log)	Doses	Dosing Schedule	Subjects
Cohort 1	VXA-G1.1-NN	1x10 ¹⁰	2	Day 1 & Week 4	10
Cohort 2	VXA-G1.1-NN	$1 x 10^{10}$	2	Day 1 & Week 8	10
Cohort 3	VXA-G1.1-NN	$1 x 10^{10}$	2	Day 1 & Week 12	10
				Total	30

Eligible participants will be enrolled to receive their first dose of study vaccine on Day 1.

During the Active period, participants will record symptoms of reactogenicity daily for 1 week post each vaccination, administered based on Cohort assignment, using a Solicited Symptom Diary. Participants will return to the site as specified in the SoA to have safety assessments and samples collected for evaluation of immunogenicity.

Additionally, female participants of childbearing potential must have a negative pregnancy test before their second dose of study drug. Participants deemed unsuitable for the second dose due to acute illness or new medical condition may be re-assessed, and if the condition resolves, may have a delayed second dose administered within 1 week of their originally scheduled second-dose visit (+7 days window). Participants with a delayed second study drug administration will follow the delayed schedule through their active period.

All participants will enter the follow-up period 4 weeks after their second dose and will be monitored for SAEs, including AESI and NOCI, through End of Study. Participants will also be evaluated for immunogenicity as specified in the SoA.

Any participants who are not eligible to receive the second study drug administration will enter the follow-up period at that visit rather than receiving the second dose and will be monitored for safety and evaluated for immunogenicity through their End of Study as specified in the SoA.

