3.0 Study Design

3.1 General study design

This is a Phase 1b, open-label, boost-optimization study to evaluate the immunogenicity, safety and tolerability of VXA-G1.1-NN with repeat-dose administration at Day 1 and varying boost schedules in healthy

adult subjects aged 18 - 55. Thirty subjects will be enrolled to one of the three treatment cohorts (10 subjects in each cohort) with varying boosting vaccination schedules at Week 4, 8 or 12, respectively, post the initial vaccination on Day 1 such that each subject will receive two doses of 1×10^{10} IU ± 0.5 log in total. See study protocol Section 5 for inclusion and exclusion criteria.

On Day 1, participants will be enrolled sequentially in order of eligibility. Participants may be assigned to cohorts based on their availability for the second dose (boost). Cohorts 3 and 2 will be enrolled prior to Cohort 1 to optimize the overall study timeline.

Group	Study Drug	Dose (IU ±0.5 log)	Doses	Dosing Schedule	Subjects
Cohort 1	VXA-G1.1-NN	1x10 ¹⁰	2	Day 1 & Week 4	10
Cohort 2	VXA-G1.1-NN	1x10 ¹⁰	2	Day 1 & Week 8	10
Cohort 3	VXA-G1.1-NN	1x10 ¹⁰	2	Day 1 & Week 12	10
				Total	30

Table 1: Treatment Arm, Doses and Sample Sizes

The study will include a Screening period, Study Period 1, Study Period 2, and a Follow-up Period:

- Screening Period (Day -45 to -1)
- Study Period 1 (Day 1 to 4 weeks post initial vaccination)
- Study Period 2 (4 weeks from the second vaccination: Week 4 to Week 8 for Cohort 1; Week 8 to Week 12 for Cohort 2; Week 12 to Week 16 for Cohort 3)
- Follow-up Period (6 months post the second vaccination for each cohort: Month 7 for Cohort 1, Month 8 for Cohort 2 and Month 9 for Cohort 3)

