3.2 Randomization and blinding

As VXA-NVV-105 is a Phase 1b, open-label, boost-optimization study to determine the immunogenicity, safety and tolerability of vaccine VXA-G1.1-NN at dose level 1×10^{10} IU ± 0.5 log with varying boosting schedules, neither randomization nor blinding will be applicable for this study. Both subjects and investigators will be aware of individual treatment assignment.

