5.0 Sample Size and Power

No formal sample size calculation was performed for the study. Thirty subjects in total (10 in each cohort) are planned to be enrolled based on experience of a typical Phase I vaccine study.

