8.6.2 Multiplicity

There will be multiple outcomes pertaining to immunogenicity; however, each outcome will be analyzed separately, and no corrections will be made to account for multiplicity. Pairwise comparisons among cohorts will also be conducted; Holm-Bonferroni method will be used to control family-wise error rate, both adjusted and unadjusted p-values will be reported.

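### Cohorts are not randomised but are tested pairwise, and covariate adjustment covers only Day 1 BT50 titre although Day 8 and Day 29 samples could be used to reduce selection bias

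*Protocol*

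**What the plan says.** **Allocation.** SAP 3.2 says "neither randomization nor blinding will be applicable for this study". Protocol section 4 says "On Day 1, participants will be enrolled sequentially in order of eligibility" and then "Participants may be assigned to cohorts based on their availability for the second dose (boost". On calendar order the two documents differ in firmness. The Protocol says "Cohorts 3 and 2 may be enrolled prior to Cohort 1 to optimize the overall study timeline"; SAP 3.1 says "Cohorts 3 and 2 will be enrolled prior to Cohort 1 to optimize the overall study timeline".

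**Comparison.** SAP 8.6.1 plans pairwise t-tests on the log scale, or Wilcoxon tests if normality fails. SAP 8.6.1.1 compares BT50 responder percentages by Fisher's exact test. SAP 8.6.1.2 adds ANCOVA contrasts for BT50. SAP 8.6.2 says "Pairwise comparisons among cohorts will also be conducted", with Holm-Bonferroni control and both adjusted and unadjusted p-values reported.

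**Adjustment.** The ANCOVA is for BT50 only, with cohort and baseline log titre as its terms. Serum IgG is also expressed as a geometric mean fold rise (SAP 4.1), which is a within-subject correction but not a covariate model. IgA ASC has neither. Demographics and baseline characteristics are tabulated (SAP 8.4), by cohort under the general convention in SAP 8.1.

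**Samples.** In both schedules, all three cohorts give PBMC on Days 1 and 8 and serum on Days 1 and 29.

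**The concern.** Cohorts differ by design only in the boost interval, and the study exists to compare intervals. If people enter a cohort because of when they can return, or because of which cohort was open when they qualified, the interval is mixed with participant type and enrolment period. A post-boost difference could then predate the boost. Holm adjustment controls chance findings across pairs; it does nothing about groups that were not comparable to begin with.

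The results are meant to inform later trials (Protocol 9.1), so a difference attributed to the interval could carry a schedule forward. Two of the three primary assays have no covariate model, and neither document says that these p-values come from non-randomised groups.

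**Working it through.** **Inputs.** Cohort size is 10 and the total 30 (SAP 3.1 and 5.0); 3 × 10 = 30 agrees. No alpha is stated for the tests; I assume two-sided 0.05, in line with the 95% CIs. The shift d, in SDs on the log scale, is an assumption, as are all correlations below. There is no power figure to reproduce: "No formal sample size calculation was performed for the study".

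**Step 1: unadjusted t-test, no true interval effect.** For 10 versus 10, df = 18 and the critical value is 2.101. The noncentrality is d × √(10/2) = d × √5. The second rejection column uses the first Holm step, 0.05/3 = 0.0167.

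| Shift d | Noncentrality | Rejects at 0.05 | Rejects at 0.0167 |
|---|---|---|---|
| 0 | 0 | 5.0% | 1.7% |
| 0.25 | 0.56 | 8.3% | 3.2% |
| 0.5 | 1.12 | 18.5% | 8.7% |
| 0.75 | 1.68 | 35.5% | 19.8% |
| 1.0 | 2.24 | 56.2% | 36.9% |

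Simulating three cohorts with one shifted (20,000 runs), the chance of at least one Holm-significant pair is about 4% with no shift, 15–16% at 0.5 SD and 53% at 1 SD.

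**Step 2: what the planned BT50 ANCOVA does.** With an assumed baseline–outcome correlation of 0.5 to 0.7, there are two extremes:
- If the shift acts wholly through baseline titre, the Cohort 1 versus 3 rejection rate stays at about 5%.
- If it comes from something else, the rate is 23–32% at 0.5 SD. The covariate shrinks the residual variance but leaves the shift in place.

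**Step 3: adding the Day 29 value.** Take d = 0.5 on both Day 29 and post-boost, absent at Day 1, with both correlations involving Day 1 equal to 0.5. Let r be the correlation between Day 29 and post-boost.
- Coefficient on Day 29: b = (r − 0.25)/0.75.
- Shift left over: 0.5 × (1 − b).
- Residual variance: 1 − (0.25 + r² − 0.5r)/0.75.

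| r | b | Shift left | Residual SD | Ratio | Rejects (simulated) |
|---|---|---|---|---|---|
| Day 1 only | – | 0.50 | 0.87 | 0.58 | about 22–24% |
| 0.5 | 0.33 | 0.33 | 0.82 | 0.41 | about 13% |
| 0.7 | 0.60 | 0.20 | 0.69 | 0.29 | about 9% |
| 0.8 | 0.73 | 0.13 | 0.59 | 0.23 | about 7% |

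Day 29 adjustment removes much of the excess when Day 29 predicts the post-boost value well, and less when it does not.

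**Step 4: why Day 29.** By then every cohort has had one identical dose, and Cohort 1 is boosted only at that visit. A cohort difference in Day 29 serum or Day 8 ASC therefore cannot be due to the interval. The sample just before boost (Day 57 in Cohort 2, Day 85 in Cohort 3) is unsuitable as a covariate, because any waning by then is part of the interval effect.

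**Step 5: precision of a comparability check.** At 10 versus 10 the 95% CI half-width is 2.101 × √(2/10) = 0.94 SD. A 0.5 SD imbalance would reach significance in only 18.5% of trials and be missed in 81.5%.

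**The case against.** A reader might infer that the SAP has no check or adjustment at all. The documents do not support that. BT50 is baseline-adjusted expressly because cohorts may differ, IgG is reported as a fold rise, and baseline data are tabulated by cohort. The ANCOVA is also fitted at each post-dose visit, so a Day 29 BT50 contrast is already planned, and Day 8 ASC and Day 29 IgG are to be summarised by visit. What is missing is the use of these values as a comparability check and as covariates.

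Four further arguments have force:
- **Selection is permitted, not shown.** The Protocol says availability and cohort order may apply, and the shift sizes above are hypothetical.
- **The calendar argument cuts both ways.** With simultaneous enrolment, Cohort 3 would be boosted 12 − 4 = 8 weeks after Cohort 1. Enrolling it first can bring the boosts closer together, although it separates the first doses.
- **The remedy is partial.** Day 29 values cannot capture exposure or assay changes arising later, and a non-significant check at this size could falsely reassure.
- **The stakes are limited.** This is an openly non-randomised Phase 1b study of 30, and Protocol 9.2.2 plans only summaries by cohort.

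These points limit the size of the concern. They do not answer the absence of a covariate model for IgG and ASC, or of any statement on how to read the p-values.

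**Conclusion.** The concern holds in limited form. Allocation is non-random, pairwise inference is planned, and covariate adjustment stops at Day 1 titre for BT50. With no interval effect, assumed shifts of 0.25, 0.5 and 0.75 SD turn a nominal 5% unadjusted test into about 8%, 19% and 36%. These figures show sensitivity; they do not estimate this trial's error rate.

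A reader might also infer that the cohorts are in fact biased, or that they should now be randomised. Neither follows. No document reports an imbalance, and Protocol Appendix 7 says enrolment is complete. The change is worth making because it uses samples already scheduled, but no confirmatory claim rests on these tests.

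**What to change.** 1. **SAP 8.6.1.2.** Extend the 28-day post-boost ANCOVA to serum IgG. Adjust BT50 and IgG for Day 1 and Day 29 log values, using Day 29 in every cohort. Adjust 7-day post-boost IgA ASC (Days 36, 64 and 92) for Day 8 ASC. Protocol 8.1 allows assays to be skipped at some timepoints, so confirm that Day 8 ASC and Day 29 BT50 and IgG are run for everyone.
2. **SAP 8.6.1.** Present the cohort contrasts for Day 8 ASC and for Day 29 BT50 and IgG as estimates with CIs, labelled as a comparability check. Do not use them as a pass/fail test.
3. **SAP 8.6.2.** State that between-cohort p-values come from non-randomised groups and are descriptive.

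The cost is a few model runs, one or two degrees of freedom per model and weaker wording. Calendar effects arising after Day 29 would remain, and the report should say so. If the database is already locked, report these analyses as post hoc in the CSR; SAP 1.0 already provides for describing and justifying deviations there.
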